6 SELECTION AND WITHDRAWAL OF SUBJECTS

6.1 Inclusion criteria

To be eligible to participate in this study, all of the following criteria must be met:

- 1. An Institutional Review Board (IRB)/Independent Ethics Committee (IEC) approved written ICF is signed and dated by the subject or legal representative prior to initiation of any study-specific activities/procedures.
- 2. Subject is considered reliable and capable of adhering to the protocol, visit schedule, and medication intake according to the judgment of the investigator.
- 3a. Subject is an ambulatory postmenopausal Chinese women, 55 to 90 years of age (inclusive) at the time of Screening. Postmenopause is defined as no spontaneous vaginal bleeding or spotting for 12 or more consecutive months prior to Screening.
- 4. Subject has a BMD T-score ≤-2.50 at the lumbar spine, total hip, or femoral neck, as assessed by the central imaging vendor at the time of Screening based on DXA scans, and using data for Caucasian women from the National Health and Nutritional Examination Survey (NHANES, 1998).

- 5. Subject must have at least 1 of following independent risk factors for fracture:
 - History of fragility fracture (except hip fracture, a severe [SQ3] vertebral fracture or more than 2 moderate [SQ2] vertebral fractures [see exclusion criteria]);
 - Parental history of hip fracture;
 - Low body weight (body mass index $\leq 19 \text{kg/m}^2$);
 - Elderly (age \geq 65 years);
 - Current smoker
- 6. Subject has at least 2 vertebrae in the L1 to L4 region and at least 1 hip that are evaluable by DXA, as assessed by the central imaging vendor.

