### 6.2 Other Baseline disease characteristics

- BMD T-score at lumbar spine, total hip and femoral neck
- BMD T-score categories at lumbar spine ( $\leq$  -3.0, > -3.0 to < -2.5, and  $\geq$  -2.5), total hip ( $\leq$ -2.5 and > -2.5) and femoral neck ( $\leq -2.5$  and > -2.5)
- BMD (g/cm²) by machine type (Hologic vs. Lunar) at lumbar spine, total hip and femoral neck
- bone turnover markers (sCTX [ng/L], P1NP [ug/L])
- years since menopause (year)
- laboratory parameters [calcium corrected by albumin, phosphorus, creatinine, serum 25 hydroxy (OH) vitamin D level, thyroid-stimulating hormone (TSH), and intact parathyroid hormone (iPTH) Total cholesterol, low-density Lipoprotein (LDL), highdensity Lipoprotein (HDL), triglycerides]
- prior osteoporosis medication use (Yes, No)
- type of osteoporosis medication use (eg. oral bisphosphonate, IV bisphosphonate, denosumab, teriparatide (TPTD), parathyroid hormone (PTH), calcitonin, strontium, fluoride, hormone replacement therapy, traditional herbal medication, activated vitamin D, SERM, vitamin K, other)
- Loading dose of vitamin D (Yes, No)
- Baseline use of calcium (Yes, No)

- 10 year probability of major osteoporotic and hip fractures based on WHO risk factor criteria (FRAX, see in Appendix 13.3) calculated with femoral neck BMD T-score
- oft any marketing authorization of any marketing thereof. 10 year probability of major osteoporotic and hip fractures based on WHO risk factor criteria (FRAX) calculated without femoral neck BMD T-score
- parental hip fracture (Yes, No, Unknown)
- glucocorticoid use (Yes, No)
- secondary osteoporosis (Yes, No)
- rheumatoid arthritis (Yes, No)
- alcohol use (Yes, No, Unknown)
- tobacco (Yes, No, Unknown)
- caffeinated beverage use (Yes, No, Unknown)

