The data after ICE#1 and ICE#2 will be handled by treatment policy strategy and will use the observed data to do analysis. COVID-19 impacted data after ICE#3, then it will be setting to missing and imputed by multiple imputation (MI) under missing at random (MAR) assumption (MI-MAR). Details of this multiple imputation analysis are outlined in Appendix 13.4. This COVID-19 impacted data includes any BMD data after treatment interrupted (exceed 70 days since previous IMP, based on PK modeling which demonstrated that BMD loss begins after 70 days without dosing) and any missing data or out of window (exceed 70 days since previous IMP) data due to Covid-19 (other than actual COVID-19 infection). Missing data other than due to COVID-19 impacted will be imputed by LOCF.

Missing baseline BMD by DXA at any anatomical site will not be imputed and evaluated for the BMD analysis. Missing postbaseline BMD will be imputed using the LOCF approach (by carrying forward the last non-missing postbaseline value prior to the missing value from the same anatomical site) in the 6-month analysis.

In all visits and including the screening visit, if duplicated DXA assessment were performed on the same visit the mean of the duplicated BMD values will be used for analysis. The corresponding

Confidential Page 32 of 89

T-score at baseline will be converted using the mean of the duplicated BMD (checking missing DXA assessment during DEMs in section 4.2).

If a subject has BMD values from different DXA machine types (ie, Hologic and Lunar) only those BMD values that are collected from the same machine type as the Baseline BMD will be used for analyses and imputation. For anatomical sites that can be measured on different body sides (ie, left and right), only those BMD values that are collected from the same body side as the Baseline BMD will be used for analyses and imputation.

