### 13.4 Multiple Imputations for BMD endpoints

First, a repeated measures Gaussian model will be fitted to the data using a Bayesian approach, with non-informative priors for the mean and variance-covariance matrix to provide a joint posterior for the parameters in this model. The repeated measures Gaussian model will include separate mean profiles for each treatment group and the same covariates as those in the primary ANCOVA analysis.

Independent samples will then be drawn from the posterior distributions for the mean and variance-covariance matrix to provide inputs into an imputation model. For each subject with missing data, these sampled values of the parameters for mean vectors and the variance-covariance matrices specify a joint distribution for their observed and unobserved outcome data.

Missing post-baseline BMD will be modelled under missing at random assumption. The ANCOVA model as in primary analysis will include fixed effects for treatment (two levels), Baseline BMD value, machine type at baseline, region, age strata group (stratification factor), and interaction of Baseline BMD value and machine type at baseline as independent variables.

The MI-MAR method will be applied as follows based on raw values:

- Step 1: Any observation after date of ICEs will be set to missing.
- Step 2: Create a dataset, one for each treatment group, of study participants with observed values and those needing estimation by multiple imputation. For the imputation step, missing values will include non-monotone missing values (ie, intermittent missing values between completed assessments) and monotone missing values (ie, where all study participant data is missing after a given time point).
  - Step 2a: First, the intermittent missing values in each dataset will be imputed using the MCMC method with multiple chains, monotone missing data imputing pattern, and non-informative priors for all parameters. Unless specified differently, the first 200 iterations will not be used (the 'burn-in' option). A total of 100 sets of imputations will be performed. The seed used for these imputations will be 2022 and all other multiple imputation procedures described in this SAP will use this same seed as well.

The resulting 100 imputed data sets will have a monotone missing data pattern and will be imputed using a method for monotone missingness:

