- Step 2b: For monotone missing data, monotone regression will be used to impute missing data. A separate regression model is estimated for each variable with missing values (ie, measurement at each time point). Based on the resulting model, a new regression model is then drawn and is used to impute the missing values for the variable. Since the data set has a monotone missing data pattern, the process is repeated sequentially for variables with missing values. The procedure will be based on the 100 imputed datasets generated from the MCMC procedure and will be performed by Imputation.
- Step 2c: If an imputed value falls outside of the pre-defined range of values for the given variable, the value will be truncated to be within the predefined range of values for the endpoint of interest.

The SAS® PROC MI procedure will be used for the imputation.

Confidential Page 49 of 89

Romosozumah

The visits to include in the MCMC and monotone regression steps will be the same, and will correspond to all data available at the time of the analysis, as specified below:

- For dry-runs conducted prior to the Month 6 analysis, all weeks up to Month 6 will be included,
- For the Month 6 analysis, all weeks up to Month 6 will be included,
- For the final analysis, all weeks up to Month 12 will be included.

The stratification factors (age strata group) may be dropped from the imputation model to facilitate model convergence if required (and this holds true for all imputation models). The post-Baseline values will need to be specified in chronological order in the imputation model so that the SAS® PROC MI imputes variables from left to right (ie, the Month 6 value will be first) imputed using regression based on Month 3, and then the Month 12 value will be imputed using regression based on Month 3 and Month 6 values, etc.).

The resulting datasets for each treatment arm will be combined into one complete dataset based on each of the 100 imputations (containing 100 times the number of study participants analyzed).

The imputation model based on the MCMC method for intermittent missing values will only allow multivariate normal variables. Therefore, region which has 3 levels will be re-coded as indicator variable:

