/***** for intermittent missing values ******/
PROC MI data=xxx NIMPUTE = 100 seed=xxx NOPRINT OUT=xxxx min=0 max=1;

BY trtp;

VAR type agegp region1 region2 base aval_m3 aval_m6;

MCMC CHAIN=multiple IMPUTE = monotone;

run;

/******* for monotone missing values *********/
proc mi data=xxx seed=xxx nimpute=1 NOPRINT out=xxxx;
var agegp trtp region machinetype base aval m3 aval m6;
class agegp trtp region machinetype
MONOTONE REGRESSION
BY imputation;
run;
PROC MIXED DATA
         BY imputation
         CLASS trtp type region agegp;
         MODEL pchg=base trtp type agegp region base*type;
         LSMEANS trtp / om cl stderr pdiff;
       ods output LSMeans=LMS Diffs=DIFF;
 *** MIANALYZE;
proc sort data=DIFF; by imputation; run;
```

This document cannot be used any extensions of variations thereof.

Confidential

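### SAP Appendix 13.4 bounds imputed raw BMD to 0–1 in its MCMC pseudo-code and never gives the Step 2c truncation range; a 0–1 range has no basis for BMD in g/cm²

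*SAP*

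**What the plan says.** SAP 8.1.1 sends COVID-19-impacted BMD data in the primary estimand to multiple imputation: "Details of this multiple imputation analysis are outlined in Appendix 13.4". Supplementary analysis 3 (SAP 8.1.2) and the hip endpoints (SAP 8.2) also use multiple imputation.

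On scale, the appendix states: "The MI-MAR method will be applied as follows based on raw values". SAP 6.2 reports BMD in g/cm² by machine type.

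The appendix then imputes in two calls:

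- The first fills intermittent gaps. It opens with "PROC MI data=xxx NIMPUTE = 100 seed=xxx NOPRINT OUT=xxxx min=0 max=1", lists "VAR type agegp region1 region2 base aval_m3 aval_m6" and runs "MCMC CHAIN=multiple IMPUTE = monotone". One pair of limits covers the 0/1 indicators and the three BMD variables alike.
- The second fills monotone gaps by regression and has no limits.

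Step 2c adds a rule in prose: "If an imputed value falls outside of the pre-defined range of values for the given variable, the value will be truncated". The text never says what that range is. The only numeric range in the appendix is the 0–1 in the first call.

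On eligibility, Protocol 6.1 requires "Subject has a BMD T-score ≤-2.50 at the lumbar spine, total hip, or femoral neck". One low site is enough, and SAP 4.6 plans a subgroup with lumbar spine T-score above -2.5.

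**The concern.** BMD in g/cm² is not a proportion, and neither document gives a reason for a ceiling of 1. A woman can qualify on the hip with a lumbar spine that is not especially low, and romosozumab is expected to raise that value by several percent. An imputed value above 1 can therefore be legitimate.

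A ceiling would act unevenly. It bites when baseline is high and the gain is large, so more often under romosozumab than under placebo, and the imputed treatment difference would shrink. In addition, the first call has limits, the second has none, and Step 2c refers to limits that are not written down. Which imputed values are altered would then depend on a programming choice.

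**Working it through.** **1. Inputs from the documents (SAP 2.6).** Planned lumbar spine difference 6.9, with SDs 5.26 (romosozumab) and 3.34 (placebo). The two historical studies showed 8.4 and 9.4. The documents state no figure that results from the 0–1 bound. The sample-size basis was therefore checked first: for the femoral neck (difference 2.0, SDs 4.39 and 4.10, n = 146 and 73, Satterthwaite t-test, two-sided 5%), power is 91.0%, which agrees with the stated minimum of 90%.

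**2. Which values the coded bound can reach.** A gap is intermittent if a later visit is observed, and monotone otherwise.

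| Analysis | Missing visits | Bounded call fills | Unbounded call fills |
|---|---|---|---|
| 6-month | Month 3 only | Month 3 | – |
| 6-month | Month 6 only | – | Month 6 |
| 6-month | Months 3 and 6 | – | Months 3 and 6 |
| Final | Month 6 only | Month 6 | – |
| Final | Months 3 and 6 | Months 3 and 6 | – |
| Final | Months 6 and 12 | – | Months 6 and 12 |

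At the 6-month analysis the coded limit touches only Month 3 values in subjects whose Month 6 is observed. Month 3 BMD is still an analysed variable: SAP 8.3 applies the derivation rules of 8.1.1 and the ANCOVA to it. The limit on baseline has no effect, because SAP 8.1.1 does not impute missing baseline BMD. A missing Month 6 value is capped at this analysis only through Step 2c, and only if its range is taken as 0–1.

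**3. Where a ceiling of 1 bites.** A subject with baseline b and percent gain g passes 1 when b > 1/(1 + g/100).

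- g = 6.9: 1/1.069 = 0.935.
- g = 9.4: 1/1.094 = 0.914.
- g = 6.9 + 1.96 × 5.26 = 17.2: 1/1.172 = 0.853.
- g = 0 (assumed placebo mean): 1.000.

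**4. Effect at one baseline, for illustration.** The cap on percent change is c = 100(1/b − 1). With z = (c − m)/s, a clipped normal has mean mΦ(z) + c(1 − Φ(z)) − sφ(z), and a redrawn one has mean m − sφ(z)/Φ(z). Take m = 6.9, s = 5.26 for romosozumab and m = 0 (assumed), s = 3.34 for placebo.

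- b = 0.90, c = 11.1: romosozumab 6.27 clipped, 4.97 redrawn; placebo about 0. Difference 6.27 or 4.97.
- b = 0.95, c = 5.3: romosozumab 3.88 or 1.61; placebo −0.08 or −0.41. Difference 3.96 or 2.02.
- b = 1.00, c = 0: the clipped placebo mean is −3.34 × φ(0) = −3.34 × 0.399 = −1.33.

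**5. Effect on the trial, if Month 6 is capped.** Assumptions not in the documents: mean baseline lumbar spine BMD 0.70–0.95 g/cm², SD 0.08–0.12, placebo mean change 0, gain independent of baseline. There were 2 million draws per arm. The shrinkage per 10% of Month 6 values imputed is 0.10 × (romosozumab loss − placebo loss). For example, at mean 0.95 and SD 0.12 under truncation: 0.10 × (5.86 − 2.55) = 0.33.

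| Mean baseline | Month 6 above 1, romosozumab / placebo | Shrinkage, truncation | Shrinkage, redraw |
|---|---|---|---|
| 0.70 | 0.5–3.2% / 0–0.8% | 0.00–0.02 | 0.00–0.03 |
| 0.80 | 6.7–14.2% / 1.0–5.3% | 0.03–0.07 | 0.06–0.11 |
| 0.85 | 17.1–24.8% / 4.0–11.3% | 0.08–0.14 | 0.14–0.19 |
| 0.90 | 34.4–38.6% / 12.2–20.9% | 0.18–0.23 | 0.27–0.30 |
| 0.95 | 53.9–55.5% / 27.9–34.0% | 0.32–0.33 | 0.41–0.43 |

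With 2:1 allocation, romosozumab supplies 76% to 97% of the capped values. No calculation was made for the hip sites.

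**The case against.** The code is labelled pseudo-code and carries placeholders. The limits sit over a list that includes 0/1 indicators, so they look like a drafting leftover and not a chosen ceiling for BMD. Step 2c speaks of a range for the given variable, which suggests variable-specific limits, and it never says 0–1. In the primary analysis multiple imputation covers only COVID-19-impacted data; other gaps use LOCF. The MMRM, the observed-case analysis and the two LOCF supplementary analyses do not rely on this imputation. Confirmatory testing belongs to the 6-month analysis, and Month 12 is descriptive.

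All of this stands, and it limits the consequence. It does not make the line right. The pseudo-code is the only numeric specification in the appendix, the coded limit reaches a planned Month 3 comparison without any help from Step 2c, and Step 2c is prose that cannot be carried out until its range is settled.

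Three stronger readings are tempting. A reader might infer that the quoted line cuts off imputed Month 6 gains in the primary analysis; the second call, which fills those values, has no limits. A reader might take the single-baseline results as the effect on the trial; those baselines are hypothetical, and the results concern imputed values only. A reader might suppose that placebo is hardly affected; near a baseline of 1.0 it is, as the clipped mean of −1.33 shows.

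**Conclusion.** The 0–1 limit is wrong as written for raw BMD, the Step 2c range is missing, and the two imputation calls disagree. As coded, the limit affects imputed Month 3 values at the 6-month analysis and possibly Month 3 or Month 6 values at the final analysis. It caps the primary endpoint only if Step 2c is run with 0–1.

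In that case the lumbar spine difference would shrink by about 0.00 to 0.33 points under truncation, or 0.00 to 0.43 under redraw, per 10% of Month 6 values imputed, against a planned 6.9. That range rests on assumed mean baselines of 0.70 to 0.95 g/cm²; the loss is negligible near 0.70 and visible only from about 0.85 upward. The documents state neither baseline BMD nor the share of data imputed, so the actual size cannot be fixed.

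The documents do not support an inference that the primary test is at risk. The bias is conservative, and at 146 and 73 subjects the planned lumbar spine difference is 6.9/√(5.26²/146 + 3.34²/73) = 6.9/0.585, about 11.8 standard errors. What is at stake is the accuracy of the estimate.

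**What to change.** In Appendix 13.4, remove min=0 max=1 for the BMD variables and make the two PROC MI calls consistent on limits. Then either delete Step 2c, or keep it with its range written out as wide plausibility limits in g/cm² specific to anatomical site and machine type. If limits are kept, report how many imputed values they altered, by arm and visit.

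The cost is one line of code and one sentence of text, with no new data. The change should be settled before the unblinding that follows the 6-month snapshot, so that the range is not chosen with treatment known.

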# 13.5 Adverse Event of Interest

# MedDRA Version 24.1

• Hypocalcemia (PTs) – Based on agreed Risk Management Plan search strategy

Adjusted calcium decreased	.10
Blood calcium decreased	
Calcium deficiency	.,,0
Calcium ionised decreased	
Chvostek's sign	
Hypocalcaemia	
Hypocalcaemic seizure	
Trousseau's sign	. 18 . 18

# • Injection Site reaction (PTs)

Administration site abscess	Administration site pallor	Injection site injury
Administration site abscess	Administration site papule	Injection site irritation
sterile	0 0 0	
Administration site anaesthesia	Administration site	Injection site ischaemia
	paraesthesia	
Administration site atrophy	Administration site phlebitis	Injection site joint discomfort
Administration site bruise	Administration site	Injection site joint effusion
X	photosensitivity reaction	
Administration site	Administration site plaque	Injection site joint erythema
calcification	7, 0,	
Administration site cellulitis	Administration site pruritus	Injection site joint infection
Administration site coldness	Administration site pustule	Injection site joint inflammation
Administration site cyst	Administration site rash	Injection site joint movement
	 	impairment
Administration site dermatitis	Administration site reaction	Injection site joint pain
Administration site discharge	Administration site reaction	Injection site joint swelling
	neonatal	
Administration site	Administration site recall	Injection site joint warmth
discolouration	reaction	
Administration site discomfort	Administration site scab	Injection site laceration
Administration site dryness	Administration site scar	Injection site lymphadenopathy
Administration site	Administration site streaking	Injection site macule
dysaesthesia		
Administration site eczema	Administration site swelling	Injection site mass
Administration site erosion	Administration site thrombosis	Injection site movement
		impairment
Administration site erythema	Administration site ulcer	Injection site necrosis

Confidential Page 53 of 89

Administration site exfoliation	Administration site urticaria	Injection site nerve damage
Administration site	Administration site vasculitis	Injection site nodule
extravasation		
Administration site fibrosis	Administration site vesicles	Injection site oedema
Administration site granuloma	Embolia cutis medicamentosa	Injection site pain
Administration site haematoma	Injected limb mobility	Injection site pallor
	decreased	.10
	Injection site abscess	
Administration site	Injection site abscess sterile	Injection site papule
haemorrhage		
Administration site	Injection site anaesthesia	Injection site paraesthesia
hyperaesthesia		0,0
Administration site	Injection site atrophy	Injection site phlebitis
hypersensitivity		61,700
Administration site	Injection site bruising	Injection site photosensitivity
hypertrichosis		reaction
Administration site	Injection site calcification	Injection site plaque
hypertrophy	Va La	
Administration site	Injection site cellulitis	Injection site pruritus
hypoaesthesia	0, 7	\ O -
Administration site indentation	Injection site coldness	Injection site pustule
Administration site induration	Injection site cyst	Injection site rash
Administration site infection	Injection site deformation	Injection site reaction
Administration site	Injection site dermatitis	Injection site recall reaction
inflammation	U' 10 S'	
Administration site injury	Injection site discharge	Injection site scab
Administration site irritation	Injection site discolouration	Injection site scar
Administration site ischaemia	Injection site discomfort	Injection site streaking
Administration site joint	Injection site dryness	Injection site swelling
discomfort		
Administration site joint	Injection site dysaesthesia	Injection site telangiectasia
effusion	 	
Administration site joint	Injection site eczema	Injection site thrombosis
erythema		
Administration site joint	Injection site erosion	Injection site ulcer
infection		
Administration site joint	Injection site erythema	Injection site urticaria
inflammation	T	T • • • • • • • • • • • • • • • • • • •
Administration site joint	Injection site exfoliation	Injection site vasculitis
movement impairment	Tr. 1. 1. 1.	T
Administration site joint pain	Injection site extravasation	Injection site vesicles
Administration site joint	Injection site fibrosis	Injection site warmth
warmth		N. 1.1
Administration site laceration	Injection site haematoma	Malabsorption from injection
		site

Confidential Page 54 of 89

Administration site	Injection site haemorrhage	
lymphadenopathy		
Administration site macule	Injection site hyperaesthesia	
Administration site mass	Injection site hypersensitivity	
Administration site movement	Injection site hypertrichosis	. (
impairment		
Administration site necrosis	Injection site hypertrophy	.10
Administration site nerve	Injection site hypoaesthesia	
damage		. 20.
Administration site nodule	Injection site indentation	
Administration site odour	Injection site induration	2
Administration site oedema	Injection site infection	-0
Administration site pain	Injection site inflammation	
7 tullillistiation site pain	injection site inflammation	X \\ \ \ \ \ \ \ \ \ \ \ \ \ \ \ \ \ \

